Two independent assessments of mNIS+7 are planned at early termination visits. If both assessments are within the same visit window the mean of the two will be used. At early terminations, in the event that only one subcomponent has been performed, the single subcomponent will be used in place of the mean value for that visit for the averaged subcomponent score.

The component scores will be computed by summing the averaged subcomponent scores and the composite scores will be computed by summing the component scores.

Imputation of missing averaged subcomponents

If a patient has completed at least part of the mNIS+7/NIS+7 at a visit then the following imputation method will be used to impute this missing assessment level data for the purposes of determining component scores for summary and analysis.

The following missing data imputation steps will be considered and will be used as described below for Groups A, B, and C:

- Step 1: If at least 50% of averaged subcomponent scores within a component are available, the missing averaged subcomponent scores will be set to equal to the mean of the patient’s other non-missing averaged subcomponent scores in that component. The component score is then calculated.
- Step 2 (baseline): In the unlikely event that there are more than 50% of the averaged subcomponents scores within a component that are missing at baseline, the missing averaged subcomponent scores will be set to equal to mean baseline averaged subcomponent score from the parent study Randomized Set (across treatment groups). The component score is then calculated.
- Step 3 (post-baseline visits): For certain components, and only under certain conditions which will be listed below, the missing averaged subcomponent scores at that visit within that component only will be set equal to the mean averaged subcomponent score among the subjects randomized to placebo in the Randomized Set at that visit. The component score is then calculated.

If a post-baseline assessment does not fall into the scheduled analysis windows, there is no obvious visit on which the mean subcomponent scores in the placebo group can be derived. In order to apply step 3, the following visits will be used to derive the mean scores in the placebo group:

Timing of Visit	Imputation rule
Before Week 35	Randomized Set mean at baseline
Between Week 35 and Week 66	Week 35 placebo mean
After Week 66	Week 66 placebo mean

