Note: when imputing missing subcomponents based on placebo mean at a specific visit, the placebo mean is derived from on-treatment assessments only (i.e., those that were done within 52 days of last dose).

The components of the mNIS+7 and NIS+7 are grouped into A, B and C based on the imputation step used, as follows. A detailed list of components by group can be found in Table 1– Table 3 in Appendix 1:

- Group A: For components with multiple subcomponents except the NCT component of +7, imputation steps 1 and 2 will be applied.

If, after applying step 1 for post-baseline visits, 6 out of the 7 components of the mNIS+7 composite score (NIS-C, NIS-R, NIS-S, NIS-W, HP, TP or NCT) are available and only one is missing at that visit, then step 3 will be applied for the missing component.

If, after applying step 1 for post-baseline visits, 4 out of the 5 components of the NIS+7 composite score (NIS-C, NIS-R, NIS-S, NIS-W, or NCT) are available and only one is missing at that visit, then step 3 will be applied for that the missing component.

Mean averaged subcomponent score used in the imputation described in step 3 are derived from the averaged subcomponent scores before step 1 imputation among the group of patients who were randomized to placebo.

If, after applying steps 1-3 as appropriate, there are still missing subcomponent scores, the component score will be set to missing.

- Group B: For the NCT component of +7, it should be noted that the following 3 of the 5 subcomponents of this component may be “not evaluable” as an additional category to missing: 1) fibular nerve motor conduction velocity (PMCVK), 2) fibular nerve distal latency (PMLA), 3) tibial nerve distal latency (TMLA) (see Table 3 in Appendix 1). These nerve conduction attributes are not evaluable when the tibial or fibular nerve amplitude is 0, therefore, these “not evaluable” results are considered informative missing results and a slightly different imputation method is applied here. The following imputation rule will be used for Nerve Conduction Tests component score of +7: The normal deviate score for PMCVK, PMLA and TMLA will be respectively set to 3.72 (the worse response) if the recorded response was classified “not evaluable.” After this, imputation step 1 and 2 will be applied.

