3.3.3 Additional Analyses of Primary Endpoints

In addition to the primary efficacy analysis, the following sensitivity analyses will be conducted on the FAS except where noted for each of the two primary efficacy endpoints:

- **Sensitivity Analysis 1 (Non-Parametric Analysis)** – The non-parametric Van-Elteren test will also be performed for the two primary study endpoints as the sensitivity analysis. Hodges-Lehmann estimates of the differences between ISIS 420915 300 mg group and the placebo group as well as distribution-free CIs based on the Wilcoxon Rank Sum Test will also be provided.
- **Sensitivity Analysis 2 (Conservative Assessment Level Imputation)** – To examine whether the primary analysis results are robust to the strategy for imputing missing assessment level data, an alternative strategy that results in a conservative estimate of the treatment effect will be implemented. Patients without an assessment at a visit will not have their score imputed for that visit. Imputation of missing baseline assessment level data will follow the approach detailed in Section 3.2.1.3. For patients with at least one non-missing post-baseline subcomponent score missing data will be imputed as follows. Missing post-baseline assessment level data will be imputed for the placebo group using their observed or imputed baseline value. Missing post-baseline assessment level data will be imputed for the ISIS 420915 group using the placebo mean in the Randomized population for that subcomponent at that visit (done after the placebo imputation).
- **Sensitivity Analysis 3 (Excluding Assessments done at Early Termination Visits)** – In order to examine the robustness of the primary analysis to the inclusion of premature termination data, the primary efficacy analysis will be repeated excluding data collected at early termination visits which are included in the primary analysis.
- Sensitivity analyses will be performed to investigate the impact of alternative missing data assumptions (see sections 3.3.3.2 and 3.3.3.3). These analyses will be done on the Safety Set and will be labeled as:
 - **Sensitivity Analysis 4** – Multiple Imputation assuming Missing at Random
 - **Sensitivity Analysis 5** – Multiple Imputation assuming Copy Increments from Reference
 - **Sensitivity Analysis 6** – Multiple Imputation assuming Jump to Reference
 - **Sensitivity Analysis 7** – Data at Withdrawal Visit Included

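### Sensitivity Analysis 2 is called conservative without condition, but its fill for the ISIS 420915 arm can mildly favour ISIS when mainly sicker treated patients miss items

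*SAP*

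**What the plan says.** SAP 3.3.3 gives Sensitivity Analysis 2 (SA2 below) this purpose: "To examine whether the primary analysis results are robust to the strategy for imputing missing assessment level data". It then claims that "an alternative strategy that results in a conservative estimate of the treatment effect will be implemented".

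The rules are:
- Wholly missed assessment: "Patients without an assessment at a visit will not have their score imputed for that visit".
- Partly completed assessment: "For patients with at least one non-missing post-baseline subcomponent score missing data will be imputed as follows".
- Placebo arm: "Missing post-baseline assessment level data will be imputed for the placebo group using their observed or imputed baseline value".
- Treated arm: "Missing post-baseline assessment level data will be imputed for the ISIS 420915 group using the placebo mean in the Randomized population", subcomponent by subcomponent at that visit, computed after the placebo fill.

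SAP 3.3.1 defines the endpoint as change from baseline to Week 66. SAP 3.3.2 adjusts for baseline.

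The primary scoring (SAP 3.2.1.3) has a related rule. Under Step 3 a missing item "will be set equal to the mean averaged subcomponent score among the subjects randomized to placebo in the Randomized Set at that visit", in either arm. For the mNIS+7 this applies only when six of the seven listed components "are available and only one is missing at that visit, then step 3 will be applied for the missing component". Group C, which covers heart rate to deep breathing (HRDB), uses the same post-baseline fill. If a component is still missing after these steps, the composite is missing.

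**The concern.** The two fills differ in kind. The placebo fill is a change of zero, which is unfavourable to ISIS 420915 in a progressive disease. The ISIS fill is a level. The change it implies is the placebo mean level minus the patient's own baseline, so the higher the baseline, the better the imputed outcome. Eligibility spans NIS scores of 10 to 130, so patients well above the mean are to be expected.

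SA2 is the check the SAP assigns to item-level imputation. If its label is taken at face value, agreement with the primary result will be read as reassurance even where the check leans towards ISIS. For an ISIS patient missing one whole component, SA2 uses the same kind of value as primary Step 3, so it does not test that choice.

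**Working it through.** **Inputs from the documents (SAP 4, SAP 3.3.1).** Planned mNIS+7 changes are +16 (placebo) and +6.4 (ISIS), SD 14, 135 patients at 2:1, 25% dropout. The modified +7 maximum is 102.32 of 346.32 points.

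**The plan's own figure.** 135 × 0.75 = 101.25, or 67.5 : 33.75. SE = 14 × √(1/67.5 + 1/33.75) = 2.95. Power is 0.902 by the normal approximation (0.896 by noncentral t), which agrees with the stated 90%. With 68 : 34, SE = 2.94. SA2 carries no figure of its own.

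**Closed form.** Let *m* be the fraction missing a part, *s* that part's share of mean change, and *X* the mean baseline excess on that part of the ISIS patients who miss it. Change is taken as unrelated to baseline. A positive shift is conservative.
- *Equal missingness.* The placebo mean change falls by 16ms. The placebo level after its own fill is the mean baseline + 16s(1 − m), so the imputed ISIS change is 16s(1 − m) − X against a true 6.4s. Shift = m[s(25.6 − 16m) − X].
- *ISIS only.* Shift = m(16s − X − 6.4s) = m(9.6s − X).

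SA2 turns anti-conservative when X exceeds:

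| Missing part | Both arms, m = 5%, 10%, 20% | ISIS only |
|---|---|---|
| One of seven equal components (s = 1/7) | 3.5, 3.4, 3.2 | 9.6/7 = 1.4 |
| Modified +7 (s = 102.32/346.32 = 0.295, assumed proportional to maximum points) | 7.3, 7.1, 6.6 | 2.8 |
| s = 0.4 | – | 3.8 |

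Illustration with s = 1/7: an ISIS patient 5 points above average on the missing component is assigned 16/7 − 5 = −2.7, an improvement. The planned ISIS change on that component is 6.4/7 = +0.9.

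**Simulation 1.** 68 : 34, Week 66 ANCOVA on baseline, 4,000 runs per cell. Assumed: 5-10% missing; baseline SD of the part 4.2, 8.4 or 12, matched to s = 1/7, 0.295 or 0.4; severity link of 0.5-1.0 log-odds per SD.

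| Missingness | SA2 shift | With own baseline + placebo mean change |
|---|---|---|
| Unrelated to severity | +0.18 to +0.96 | conservative |
| Severity-linked, both arms | −0.03 to +0.44 | +0.18 to +1.02 |
| Severity-linked, ISIS only | −0.58 to −0.03 | +0.07 to +0.39 |

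A mismatched limiting pair (SD 12 with s = 1/7) gives −0.60 to −0.10 in both arms and −0.80 to −0.20 for ISIS only.

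The closed form agrees. At m = 0.10 for the modified +7 with X = 6.82:
- Both arms: 0.1(0.295 × 24 − 6.82) = +0.03; simulated +0.03.
- ISIS only: 0.1(2.84 − 6.82) = −0.40; simulated −0.38.

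**Simulation 2, a different set-up.** Eight equal components, composite baseline SD 20, 30 or 40 (assumed). Except in the first case, 30% of the sickest third miss items. True effect −9.6.
- Random 10%, both arms, one component: −9.27, −9.25, −9.30 (conservative).
- Sickest third, both arms, one component: −9.59, −9.73, −9.84.
- Sickest third, ISIS only, one component: −9.74, −9.84, −10.00.
- Sickest third, ISIS only, two components: −9.88, −10.19, −10.48.

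In the second case at SD 30, primary Step 3 scoring gives −9.53. The supposedly conservative analysis then shows the larger effect. The alternative fill stayed between −8.9 and −9.5 throughout.

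**Why the alternative fill works.** The imputed ISIS change becomes 16s for every patient, so X drops out. Shift = 25.6ms (both arms) or 9.6ms (ISIS only), positive under the planning means.

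**The case against.** **Other analyses cover part of this.** When a visit has NIS done but the modified +7 not done, the primary composite is missing. Sensitivity Analyses 4 to 6 impute it with a model that carries baseline, and Sensitivity Analysis 10 counts missing Week 66 data as non-response. This stands. It leaves uncovered the partly missing items that the primary scores under Step 3 or Group C. Sensitivity Analysis 12 removes HRDB only.

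**Item loss may be small.** Week 66 has two assessments, and an averaged subcomponent is missing only if both are (SAP 3.2.1.3). Shifts scale with m: at 2% missing, the modified +7 ISIS-only case falls to 0.02 × (2.84 − 6.82) = −0.08. This stands for Week 66; Week 35 has a single assessment.

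**Loss mainly in one arm needs a reason.** The study is double-blind and the NIS evaluator is insulated from adverse events (Protocol 4.4, 6.1.1). The documents give no mechanism for severity-linked loss confined to ISIS patients. The modified +7 pre-processing rules are redacted. Where the SAP's rules are visible, non-evaluable +7 nerve conduction values are set to the worst score. This stands as a limit on likelihood.

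**A reader might take the interim material as evidence of the pattern.** The DSMB plan (SAP 8.3, Endpoints) calls the modified +7 dataset incomplete. Its section on interpreting the unblinded results attributes missing mNIS+7 data to results not yet entered or not yet sent. That is data lag, not severity-linked item loss.

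None of this makes the unconditional label correct.

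**Conclusion.** The rule does not guarantee the conservatism that the SAP claims. The direction follows from the text; only the size needs assumptions. Under the matched assumptions at 5-10% missing:
- unrelated to severity: conservative;
- severity-linked equally in both arms: roughly neutral to conservative;
- mainly sicker ISIS patients: anti-conservative by about 0.03 to 0.6 points.

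Wider assumed baseline spreads push the both-arms case slightly anti-conservative and the ISIS-only case somewhat further. Every shift computed at the planned effect is under 1 point, against 9.6 with SE about 2.9. This is a minor point, and the primary conclusion is not expected to change. Baseline SDs, item-missing rates and the strength of the severity link are assumed, and a single-visit ANCOVA stood in for the MMRM.

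Two stronger readings are not supported:
- *That SA2 generally favours ISIS.* It does not when missingness is random, nor materially when it is balanced under matched assumptions.
- *That the primary score must be reworked because Step 3 and Group C use the same level fill.* Under no true effect with severity-linked ISIS-only loss, two-sided rejection in Simulation 1 was 0.045 to 0.056, with Monte Carlo SE about 0.0034, so no clear inflation. In Simulation 2 with one component missing, rejection in favour of ISIS was 3.1% to 4.0% against 2.5%, but only under one-sided loss that the documents give no reason to expect.

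**What to change.** In Sensitivity Analysis 2 only:
- **ISIS 420915 patients:** impute a missing post-baseline subcomponent as own baseline (observed or imputed) plus the observed placebo mean change in that subcomponent at that visit. Calculate that mean change before the placebo imputation, and keep the result within the item range.
- **Placebo patients:** keep own baseline.

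Report by arm and visit the number of patients imputed under Step 3, Group C and Sensitivity Analysis 2, with their baseline scores. That table shows whether the harmful pattern occurred. Leave primary Step 3 and Group C scoring unchanged.

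Cost: SAP wording, a small scoring-program change before unblinding, and one table. No new data are needed, since own baseline is already the fill value for placebo patients.

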2.1 General Overview of Procedures

The study consists of the following periods:

- <6 week screening and baseline assessment period
- 65 week treatment period
- 1 week EOT efficacy assessment period
- 6 month post-treatment evaluation period (unless patients elect to enroll in an OLE study in which case they will not participate in the post-treatment evaluation period)

Screening assessments include safety and specialty labs, physical exam, vital signs, electrocardiogram (ECG), and body weight. A NIS assessment is also performed that is used solely for patient eligibility purposes.

The primary endpoints (mNIS+7 and Norfolk QOL-DN questionnaire) are measured at baseline, Week 35, and Week 66 (EOT efficacy assessment). Patients who do not enroll in the OLE will also have efficacy assessments measured at Week 91 in the post-treatment evaluation period. The mNIS+7 assessments at baseline and Week 66 are performed twice and the duplicates averaged. The duplicates cannot be performed on the same day. In addition, patients who terminate treatment early for any reason will have the mNIS+7 (2x) and Norfolk QOL-DN questionnaire conducted within 14 days from the last dose of Study Drug.

Other secondary and exploratory efficacy measurements (including the pharmacodynamic measures TTR and RBP4, BMI, mBMI, and NT-proBNP) are measured at baseline, at the end of treatment (Week 65) and periodically throughout the treatment period. The SF-36 questionnaire and PND score are measured at baseline, Week 35, and Week 65.

In addition to ECHOs conducted at Baseline, early termination, and Week 65 for all patients, patients who qualify and consent to participate in the ECHO subgroup will have an additional ECHO conducted during the treatment period at Week 41, which can be done at Week 47 if the patient elects to have a Home Healthcare visit at Week 41. All ECHO assessments have a window of ± 2 weeks.

Patients participating in the PK subgroup will have additional blood draws on Day 1, Week 35, and Week 65 to evaluate pharmacokinetic and other safety parameters. PK subgroup patients will also have additional visits to collect 24 hr, 3 day, and 7 day post-dose blood draws.

Safety labs, adverse events (AEs), concomitant medications, ECGs, electroretinograms (ERGs), Ophthalmology examination, physical examination, vital signs, and specialty labs, etc. are collected periodically throughout the baseline, treatment, and post-treatment evaluation periods.

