3.2.2 Subject Populations Analyzed

The following analysis populations are defined for this study:

- Screened patients will be defined as those patients who signed an informed consent form.
- The Randomized Set will be defined as those screened patients who received a randomization assignment. Results will be summarized under the treatment to which patients were randomized.
- The Full Analysis Set (FAS) will include all randomized patients who received at least 1 injection of Study Drug (ISIS 420915 or placebo) and who have a baseline and at least one post-baseline efficacy assessment for the mNIS+7 score or Norfolk QOL-DN questionnaire total score. This will be the primary population for analysis of efficacy and PD outcomes. Results will be summarized under the treatment to which patients were randomized.
- The Safety Set (SS) will include all randomized patients who received at least 1 injection of Study Drug. This population will be used for analyses of all safety measures. Results will be summarized under the treatment which the patients received.
- The Per-Protocol Set (PPS) will include the subset of the Full Analysis Set who have received at least 80% of the prescribed doses of Study Drug and who have no major protocol violations that would be expected to affect efficacy assessments. Prescribed doses of Study Drug mentioned above is defined as the total assigned dose in mg from the Week 1 to the last dose within this study, i.e. $300\text{mg} \times 67\text{doses} = 20100\text{mg}$. This will be a secondary population for efficacy and PD analyses and will be used for sensitivity purposes. The detailed criteria and definitions for major protocol violations will be specified and finalized prior to unblinding; individual subjects will be identified as meeting the violation criteria or not after locking the database and prior to unblinding. Results will be summarized under the treatment which the patients received.
- PK Set will include all subjects who are randomized and receive at least one dose of active Study Drug (ISIS 420915) and have at least one evaluable PK sample collected and analyzed with reportable result. Results will be summarized under the treatment which the patients received.

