3.3 Primary Analysis

3.3.1 Primary Endpoint Definition

There are two primary endpoints. The primary efficacy endpoints are the change from baseline to Week 66 in the mNIS+7 score and in the Norfolk QOL-DN questionnaire total score.

The mNIS+7 composite score has a maximum of 346.32 points. It can be broken into two components: the NIS component (maximum of 244 points) and the modified +7 component (maximum of 102.32 points). It can be further divided into the following 8 components: cranial nerves, muscle weakness, reflexes, sensory, heart rate deep breathing, nerve conduction, touch-pressure sensory, and heat-pain sensory.

The normal deviates (nds) from heart rate deep breathing and nerve conduction will be used in calculation of mNIS+7 for the primary analysis.

The mNIS+7 assessment is conducted at baseline (2 times), Week 35, Week 66 (2 times), and Week 91 (post-treatment). For visits where repeated assessments are done, the average will be used for analysis. Subcomponent scores will be averaged first, and the average composite score will be computed by summing the averaged subcomponent scores. Visits occurred after 52 days from the last dose of study medication are considered part of the post-treatment evaluation period, the data collected in the those visits will not be included in the efficacy analysis.

There are two scheduled visits for each of the two primary endpoints: Week 35 and Week 66. The data will be assigned to Week 35 or Week 66 according to the visit windows defined in section 3.2.1.3.

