- **Sensitivity Analysis 8 (Per Protocol Set)** – The primary efficacy analysis will be repeated, using the PPS population.

- **Sensitivity Analysis 9** (Adjustment for Pooled Site) – The primary efficacy analysis will be repeated, but with the addition of pooled investigative site as a fixed categorical effect in the model. In the event that there are model convergence issues, results from this analysis will not be provided and will be noted in the study report. The interaction between treatment and pooled site will also be examined if model convergence permits.
- **Sensitivity Analysis 10** (Responder Analysis) – A responder analysis based on the change in mNIS +7 score will be conducted to examine whether improvement in response is consistent over a range of response thresholds. A responder is defined as a patient whose mNIS +7 score change from baseline to Week 66 is less than or equal to the threshold value. The relationship between response rate and thresholds will be summarized using a cumulative distribution plot. In addition, comparison of response rates for specific threshold values will be done. Thresholds that will be tested will include 0, 2, 4, 6, 8, 10, 15, 20, 30 points above the baseline value. For each of these specific response thresholds, the response rates at Week 66 for both the treated group and the placebo group will be calculated and plotted against the response threshold. Patients that terminate treatment early irrespective of the reason or had missing Week 66 data will be considered a non-responder. The difference in the estimated response rate and associated 95% CI based on the Mantel-Haenszel approach will be presented for each threshold.
- **Sensitivity Analysis 11** (HRDB and Nerve Conductions Scored Using Points and NIS-Sensation Excluded) – Additional sensitivity analysis on mNIS+7 composite score will be performed using the points (instead of Normal Dev) from heart rate deep breathing and nerve conduction and also removing the sensation part of the NIS.
- **Sensitivity Analysis 12** (HRDB Component Excluded) – Additional sensitivity analysis on mNIS+7 composite score will be performed, with HRDB not included as a component. HRDB will also be descriptively summarized for the group that has least one non-imputed HRDB score during efficacy treatment period and a non-imputed score at baseline.

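### Sensitivity Analysis 10 counts every early stopper as a non-responder, but its default set, the FAS, leaves out those with no post-baseline efficacy assessment

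*SAP*

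**What the plan says.** SAP 3.3.3 opens by setting a default population: "the following sensitivity analyses will be conducted on the FAS except where noted for each of the two primary efficacy endpoints". Two departures from it are noted. For Sensitivity Analyses 4 to 7 the SAP says "These analyses will be done on the Safety Set and will be labeled as", and Sensitivity Analysis 8 uses the Per-Protocol Set. Sensitivity Analysis 10, the responder analysis on change in mNIS+7, notes no other set.

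The classification rule for Sensitivity Analysis 10 is: "Patients that terminate treatment early irrespective of the reason or had missing Week 66 data will be considered a non-responder". Response rates are plotted and compared at nine thresholds from 0 to 30 points above baseline, with Mantel-Haenszel differences and 95% CIs.

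SAP 3.2.2 limits the FAS to dosed patients "who have a baseline and at least one post-baseline efficacy assessment for the mNIS+7 score or Norfolk QOL-DN questionnaire total score". The Safety Set has no such condition: "The Safety Set (SS) will include all randomized patients who received at least 1 injection of Study Drug". It is, however, summarised by treatment received, whereas the FAS is summarised by treatment assigned.

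On timing, SAP 3.3.1 says: "There are two scheduled visits for each of the two primary endpoints: Week 35 and Week 66". Under SAP 2.1, "patients who terminate treatment early for any reason will have the mNIS+7 (2x) and Norfolk QOL-DN questionnaire conducted within 14 days" of the last dose.

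**The concern.** The classification rule covers every patient who stops, whatever the cause. The default population is narrower, because membership depends on an efficacy assessment obtained after randomization. A patient who stops before Week 35 and is never assessed meets the rule for non-response but is outside the set to which the rule is applied.

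At stake is how far the response rates can be trusted as rates in which stopping counts as failure. Patients who die or leave the study early are the ones such an analysis most needs to keep. Removing them raises the response rate in their arm at every threshold where that arm has responders. The comparison also becomes conditional on a post-randomization event that may differ between arms.

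**Working it through.** **Who is lost.** Setting the provisions side by side for a dosed patient with a baseline:

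| Patient | In FAS? | Result in Sensitivity Analysis 10 |
|---|---|---|
| Stops before Week 35, completes mNIS+7 or Norfolk at early termination | Yes | Non-responder, as intended |
| Stops after a Week 35 assessment | Yes | Non-responder, as intended |
| Stays on treatment, assessed at Week 35, Week 66 missing | Yes | Non-responder, as intended |
| Stops before Week 35, no early-termination efficacy assessment | No | Absent from numerator and denominator |

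Only the last row conflicts with the rule. FAS membership does not require in-window data: the rerandomization steps in SAP 3.3.2 refer to FAS patients whose post-baseline data may fall outside a window. A late early-termination assessment therefore still keeps a patient in.

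**Effect on the rates.** Suppose an arm has N dosed patients and response rate p when all are counted, and x unassessed non-responders are dropped. Its rate becomes pN/(N − x). The difference, active minus placebo, changes by

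p_A·x_A/(N_A − x_A) − p_P·x_P/(N_P − x_P).

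The first term is positive when active patients are lost. The second subtracts when placebo patients are lost.

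**Illustration 1.** N is 90 and 45 (SAP 1.1). Response rates of 40% (36/90) and 20% (9/45) are assumed. The documents do not give the number lost, so 2 to 8 active and 1 to 3 placebo are assumed.

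| Lost, active / placebo | Active | Placebo | Difference (points) |
|---|---|---|---|
| 0 / 0 | 36/90 = 40.0% | 9/45 = 20.0% | 20.0 |
| 2 / 3 | 36/88 = 40.9% | 9/42 = 21.4% | 19.5 |
| 6 / 3 | 36/84 = 42.9% | 9/42 = 21.4% | 21.4 |
| 5 / 1 | 36/85 = 42.4% | 9/44 = 20.5% | 21.9 |
| 8 / 2 | 36/82 = 43.9% | 9/43 = 20.9% | 23.0 |

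**Illustration 2, on the SAP's planning values.** The SAP gives no figure for the responder analysis, so the inputs come from SAP section 4: mean changes 6.4 and 16, SD 14, dropout 25%. They reproduce the stated power. With 67.5 and 33.75 completers, the SE is 14·√(1/67.5 + 1/33.75) = 2.95 and 9.6/2.95 = 3.25. Power is 0.902 by the normal approximation and 0.896 by the t-test, against the stated 90%.

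Assume normal changes and count all dropouts as non-responders. The response rate at threshold c is then 0.75·Φ((c − mean)/14). At c = 10 this is 0.75 × 0.601 = 45.1% for active and 0.75 × 0.334 = 25.1% for placebo. Differences below are in points, from unrounded rates; a 10% loss is 9 of 90 or 4.5 of 45.

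| Threshold | None lost | 10% of both arms | 10% of active only | 10% of placebo only |
|---|---|---|---|---|
| 0 | 14.8 | 16.4 | 17.5 | 13.7 |
| 10 | 20.1 | 22.3 | 25.1 | 17.3 |
| 30 | 8.5 | 9.4 | 16.4 | 1.4 |

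A 10% loss in one arm is chosen to show the range. It is not a forecast.

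**The case against.** The strongest reply is that the gap is narrow. Early-termination mNIS+7 and Norfolk assessments are planned for everyone who stops. Protocol 6.1.3 asks for them as soon as possible if the 14 days are missed, and 8.9 has a separate provision after liver transplant. Either instrument is enough for FAS membership. This stands, and it limits the point to patients who miss both. It does not close the gap: protocol 8.8 asks for every effort, not certainty, 8.9 ends observation at once when consent is withdrawn, and a patient who dies cannot attend.

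It can also be said that a rule applied inside a stated set is not contradictory, that this is one of 13 sensitivity analyses with no role in the primary test, and that SAP 3.2.3 already tabulates FAS and Safety Set counts by arm. In Illustration 1 the 95% CI half-width is about 15 points (SE = √(0.4·0.6/90 + 0.2·0.8/45) = 7.9 points), well above the shifts shown. These points bear on importance. They do not make the reported rates follow the rule as written.

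A reader might infer four stronger claims that the documents do not support:

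- That the earliest treatment failures are excluded as a class. Those who complete either assessment are kept and counted.
- That the error favours the drug. Equal proportional loss does widen a positive difference, but losing 2 active and 3 placebo patients narrows it to 19.5. Losing more active patients by count is not decisive either: on the SAP's planning values at threshold 30, losing 5 and 3 gives 75.8% against 67.6%, or 8.2 points against 8.5.
- That Sensitivity Analyses 4 to 7 use the Safety Set because of this problem. The SAP says only that they examine other missing-data assumptions.
- That this is the only test of whether the effect survives discontinuation. The copy-increment and jump-to-reference analyses also address it, on the Safety Set.

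**Conclusion.** The point holds in its narrow form. As written, dosed patients who stop before Week 35 and have no early-termination efficacy assessment are left out of Sensitivity Analysis 10, although its own rule calls them non-responders.

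Each exclusion inflates that arm's response rate. The effect on the treatment difference depends on the relative loss in the two arms and on their response rates, so neither its sign nor its size can be fixed in advance. In the first illustration the difference runs from 19.5 to 23.0 points across the scenarios shown, against 20.0 with everyone counted. That rests on assumed response rates and assumed numbers lost. The real number is probably small, because an assessment is planned for every early stopper.

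The change is worth making because it removes selection on a post-randomization event at almost no cost. It concerns one sensitivity analysis and leaves the primary test as it is.

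**What to change.** State in SAP 3.3.3 that Sensitivity Analysis 10 is conducted on the Safety Set, summarised by randomized treatment, and that patients with no post-baseline assessment are non-responders at every threshold. The words on randomized treatment are needed because SAP 3.2.2 otherwise summarises the Safety Set by treatment received. Use the same denominator for the response-rate plot and for the Mantel-Haenszel differences and CIs.

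The cost is one line of text before unblinding, with no new data and no imputation model. Response rates will be slightly lower in any arm that has such patients. If there are none, the change adds no unassessed non-responders.
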